8.3.2 DEFINITION OF SERIOUS ADVERSE EVENTS (SAE)

An adverse event (AE) or suspected adverse reaction is considered "serious" if, in the view of either the investigator or sponsor, it results in any of the following outcomes:

- Death
- A life-threatening adverse event
- Inpatient hospitalization or prolongation of existing hospitalization
- A persistent or significant incapacity or substantial disruption of the ability to conduct normal life functions, or
- A congenital anomaly/birth defect

Important medical events that may not result in death, be life-threatening, or require hospitalization may be considered serious when, based upon appropriate medical judgment, they may jeopardize the participant and may require medical or surgical intervention to prevent one of the outcomes listed in this definition. Examples of such medical events include allergic bronchospasm requiring intensive treatment in an emergency room or at home, blood dyscrasias or convulsions that do not result in inpatient hospitalization, or the development of drug dependency or drug abuse.

SAEs will be captured from the time of informed consent until 30 days after the last dose of investigational product. For information on SAE reporting and associated procedures and forms, refer to the study Safety Plan.

8.3.3 CLASSIFICATION OF AN ADVERSE EVENT

8.3.3.1 SEVERITY OF EVENT

All AEs will be assessed for severity by the investigator or designated sub-investigator. The severity of all AEs will be graded according to the National Cancer Institute Common Terminology Criteria for Adverse Events (NCI CTCAE v. 5.0)

https://ctep.cancer.gov/protocolDevelopment/electronic_applications/docs/CTCAE_v5_Quick_Reference_5x7.pdf

For adverse events (AEs) not included in the CTCAE, the following guidelines will be used to describe severity.

- **Mild** – Events require minimal or no treatment and do not interfere with the participant's daily activities.

- **Moderate** – Events result in a low level of inconvenience or concern with the therapeutic measures. Moderate events may cause some interference with functioning.
- **Severe** – Events interrupt a participant’s usual daily activity and may require systemic drug therapy or other treatment. Severe events are usually potentially life-threatening or incapacitating. Of note, the term “severe” does not necessarily equate to “serious”.

8.3.3.2 RELATIONSHIP TO STUDY INTERVENTION

All adverse events (AEs) must have their relationship to study intervention assessed by the Investigator who examines and evaluates the participant based on temporal relationship and his/her clinical judgment. The degree of certainty about causality will be graded using the categories below. In a clinical trial, the study product must always be suspect.

- **Definitely Related** – There is clear evidence to suggest a causal relationship, and other possible contributing factors can be ruled out. The clinical event, including an abnormal laboratory test result, occurs in a plausible time relationship to study intervention administration and cannot be explained by concurrent disease or other drugs or chemicals. The response to withdrawal of the study intervention (dechallenge) should be clinically plausible. The event must be pharmacologically or phenomenologically definitive, with use of a satisfactory rechallenge procedure if necessary.
- **Probably Related** – There is evidence to suggest a causal relationship, and the influence of other factors is unlikely. The clinical event, including an abnormal laboratory test result, occurs within a reasonable time after administration of the study intervention, is unlikely to be attributed to concurrent disease or other drugs or chemicals, and follows a clinically reasonable response on withdrawal (dechallenge). Rechallenge information is not required to fulfill this definition.
- **Possibly Related** – A clinical event, including an abnormal laboratory test result, whose temporal relationship to study intervention administration makes a causal relationship possible, but improbable, and in which other drugs or chemicals or underlying disease may provide plausible explanations. There is some evidence to suggest a causal relationship (e.g., the event occurred within a reasonable time after administration of the trial medication) or a temporal relationship cannot be ruled out. However, other factors may have contributed to the event (e.g., the participant’s clinical condition, other concomitant events).
- Note: Although an AE may rate only as “possibly related” soon after discovery, it can be flagged as requiring more information and later be upgraded to “probably related” or “definitely related”, as appropriate.*
- **Not Related** – The AE is completely independent of study intervention administration (e.g., the event did not occur within a reasonable time after administration of the study intervention), and/or evidence exists that the event is definitely related to another etiology. There must be an alternative, definitive etiology documented by the clinician.

8.3.3.3 EXPECTEDNESS

The principal investigator will be responsible for determining whether an adverse event (AE) is expected or unexpected; however, sponsor will make the final determination for reporting purposes to regulatory

authorities. An AE will be considered unexpected if the nature, severity, or frequency of the event is not consistent with the risk information previously described for the study intervention.

8.3.4 TIME PERIOD AND FREQUENCY FOR EVENT ASSESSMENT AND FOLLOW-UP

The occurrence of an adverse event (AE) or serious adverse event (SAE) may come to the attention of study personnel during study visits and interviews of a study participant presenting for medical care, or upon review by a study monitor.

All AEs including local and systemic reactions not meeting the criteria for SAEs will be captured on the appropriate electronic case report form (eCRF). Information to be collected includes event description, time of onset, clinician's assessment of severity, relationship to study product (assessed only by those with the training and authority to make a diagnosis), and time of resolution/stabilization of the event. All AEs occurring while on study must be documented appropriately regardless of relationship. All AEs will be followed to adequate resolution.

Any medical condition that is present at the time that the participant is screened will be considered as baseline medical history and not reported as an AE. However, if the study participant's condition deteriorates at any time during the study, it will be recorded as a new AE.

Changes in the severity of an AE will be documented to allow an assessment of the duration of the event at each level of severity to be performed. AEs characterized as intermittent require documentation of onset, severity, and duration of each episode.

The principal investigator or designee will record all reportable events with start dates occurring any time after informed consent is obtained until 7 (for non-serious AEs) or 30 days (for SAEs) after the last dose of study drug. At each study visit, the investigator will inquire about the occurrence of AE/SAEs since the last visit. Events will be followed for outcome information until resolution or stabilization. A final follow-up phone call will be performed at Day 45 in order to assess status of any ongoing AEs or SAEs. Any AEs that are considered unresolved at Day 45 will be followed clinically by the investigator until resolution or stabilization.

8.3.5 ADVERSE EVENT REPORTING

Adverse Event

An AE is any unfavorable and unintended sign, symptom, or disease temporally associated with the use of an investigational medicinal product (IMP) or other protocol-imposed intervention, regardless of attribution. This includes the following:

1. AEs not previously observed in the subject that emerge during the protocol-specified AE reporting period, including signs or symptoms that were not present prior to the AE reporting period
2. Pre-existing medical conditions judged by the investigator to have worsened in severity or frequency or changed in character during the protocol-specified AE reporting period

3. Abnormal laboratory values or test results constitute adverse events only if they induce clinical signs or symptoms and are considered clinically significant

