7 STUDY INTERVENTION DISCONTINUATION AND PARTICIPANT DISCONTINUATION/WITHDRAWAL

7.1 DISCONTINUATION OF STUDY INTERVENTION

Discontinuation of investigational product does not mean discontinuation from the study, and remaining study procedures should be completed as indicated by the study protocol. If a clinically significant finding is identified (including, but not limited to changes from baseline) after enrollment, the investigator or qualified designee will determine if any change in participant management is needed. Any new clinically relevant finding will be reported as an adverse event (AE).

The data to be collected at the time of study intervention discontinuation will include the following:

- Reason for discontinuation
- Adverse events
- Changes to concomitant medications

If a participant discontinues investigational product, all study visits will continue as per the Schedule of Assessments (SOA).

Participants who are randomized but who subsequently have a negative RT-PCR Covid-19 test, will discontinue investigational product, but will continue to be followed up for safety and efficacy.

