8.3 ADVERSE EVENTS AND SERIOUS ADVERSE EVENTS

8.3.1 DEFINITION OF ADVERSE EVENTS (AE)

Adverse event is defined as any untoward medical occurrence associated with the use of an intervention in humans, whether or not considered intervention-related (21 CFR 312.32 (a)).

For this study, adverse events will be captured from the time of informed consent until 7 days after last dose of investigational product (30 days after last dose for SAEs)

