## **5.3.6 Safety Analyses**

Safety will be evaluated by summary of adverse events. Adverse event incidence rates will be summarized for each study arm, namely, Active Drug and Placebo Arms, in terms of severity and its relationship to study drug. A tabulation of Serious Adverse Events (SAEs) will be provided within each study arm with the number of patients experiencing a given AE or ADE, and the number of episodes while on study. Similar reports will be generated for AE monitoring purposes for the entire study cohort without unblinding of the study participants while the study is still ongoing.

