## 7.6 Interim Analysis and Data Monitoring

There is no planned interim analysis for the primary objective of the study; however, there will be safety interim analyses after the initial cohort of 12 patients have been enrolled and have received at least one dose of the assigned drug. This safety interim analysis will be conducted without unblinding the patients. As part of this safety interim analysis, if two or less number of patients in this initial cohort of 12 patients experience Grade 3+ adverse events attributable to the study regimen and not resolved through symptomatic treatments within 48 hours, there will be no need for unblinding the safety cohort; however, if there are 3 or more cases with Grade 3+ adverse events attributable to the study regimen and not resolved through symptomatic treatments within 48 hours, the enrollment will be halted, this initial cohort of patients will be unblinded to evaluate the distribution of the AEs between the placebo and the study drug, and the possible corrective amendments will be considered.

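### Protocol 8.3.5 makes a laboratory abnormality an AE only if it causes symptoms, contradicting 7.1; symptom-free liver-test rises may escape the AE-based safety comparison and the halting count

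*Protocol*

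**What the plan says.** Protocol 8.3.5, item 3, sets the only rule written specifically for laboratory results: "Abnormal laboratory values or test results constitute adverse events only if they induce clinical signs or symptoms and are considered clinically significant".

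Other sections are wider. Protocol 7.1: "Any new clinically relevant finding will be reported as an adverse event (AE". Protocol 8.3.1: "Adverse event is defined as any untoward medical occurrence associated with the use of an intervention in humans, whether or not considered intervention-related". Neither asks for symptoms.

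Protocol 8.5 gives four ALT/AST criteria at which stopping treatment will be considered. It does not say whether a participant who meets one has an AE.

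The safety endpoint (SAP 4.2) counts adverse events, related reactions and hospitalizations. Safety is the fifth secondary objective in the Protocol but the second primary objective in SAP 3.6, with its own estimand in SAP 5.3.2. On analysis, SAP 5.3.6 opens: "Safety will be evaluated by summary of adverse events". No laboratory table is named there or in the list of outputs in SAP 7.9. SAP 5.1 promises summaries of safety variables, but only as appropriate.

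The halting rule (Protocol 9.4.4 and 10.1.2, SAP 7.6) acts "if there are 3 or more cases with Grade 3+ adverse events attributable to the study regimen" in the first 12 participants, provided the events have not resolved with symptomatic treatment within 48 hours.

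**The concern.** Chemistry, haematology and coagulation tests are drawn at Day 7 and Day 14, yet the Protocol gives two answers on when an abnormal result becomes an AE. Under 8.3.5 a participant could be taken off study drug for a liver-test rise and appear nowhere in the AE table. Under 7.1 the same participant would appear. Two sites could each follow the Protocol and record the same event differently, in a trial of 52 to 60 participants at about two to four sites.

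The safety comparison, the halting count and the ongoing blinded safety reports in SAP 5.3.6 all take AEs as their input, so inconsistent recording carries through to each of them. There is no data monitoring board (Protocol 10.1.6). Laboratory tables produced at the end could repair the comparison between arms, but not a signal missed during enrolment.

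**Working it through.** The documents state no operating characteristic for the halting rule, so there is no figure to reproduce. The check is mainly one of reading.

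**1. The definitions side by side, for a symptom-free but clinically significant laboratory result**

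- 8.3.5, item 3: not an AE, because both conditions are required.
- 7.1: an AE, once the finding is clinically relevant.
- 8.3.1: an AE, if the result is taken as an untoward medical occurrence.

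Sections 8.3.5 and 7.1 cannot both be followed. Section 8.3.1 fits poorly with 8.3.5.

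**2. Which 8.5 criteria can be met without symptoms**

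- ALT or AST above 8 times ULN: no symptoms needed.
- Above 5 times ULN for more than 2 weeks: no symptoms needed, though hard to reach within a 14-day course.
- Above 3 times ULN with total bilirubin above 2 times ULN or INR above 1.5: no symptoms needed.
- Above 3 times ULN with listed symptoms, signs or eosinophilia: a clinical feature is usually present.

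Three of the four therefore need no symptoms.

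**3. One case followed through**

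Take a participant with Day 7 ALT above 8 times ULN and no symptoms.

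- Protocol 8.5: stopping treatment is considered.
- Protocol 7.2: if treatment stops, the reason goes into the eCRF. That section lists a laboratory abnormality separately from a clinical AE.
- SAP 4.2 and 5.3.6: counted only if recorded as an AE.
- Halting rule: counted only if recorded as an AE, then graded 3 or higher, judged attributable, and unresolved under the 48-hour condition. Grading comes after classification: "The severity of all AEs will be graded according to the National Cancer Institute Common Terminology Criteria for Adverse Events". The 48-hour condition has no clear meaning when there is no symptom to treat.

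**4. Illustration of the effect on the halting count**

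Assumptions: six active and six placebo among the first 12; a rate q of silent qualifying events on active drug and none on placebo; no other qualifying events; every counted event is Grade 3+, attributable and meets the 48-hour condition; all 12 participants are observed. The rate q is not in the documents.

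P(3 or more) = 1 − (1−q)^6 − 6q(1−q)^5 − 15q²(1−q)^4

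At q = 0.20: 1 − 0.2621 − 0.3932 − 0.2458 = 0.0989.

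| q | If counted | If not counted |
|---|---|---|
| 10% | 1.6% | 0% |
| 20% | 9.9% | 0% |
| 30% | 25.6% | 0% |
| 50% | 65.6% | 0% |

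Adding 5% other qualifying events in each arm, with active rate 1 − 0.95(1−q) and placebo rate 0.05, gives 10.2%, 24.3%, 41.9% and 76.0% if counted, against a constant 2.0% if not.

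The split of the first 12 can vary, because randomization is blocked within site. At q = 30% and no other events, four active participants give 8.4% and eight give 44.8%.

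**The case against.** The strongest reply is that exclusion is not certain. Section 7.1, supported by 8.3.1, would make a clinically relevant silent rise an AE, and a site that follows it loses nothing. This stands: the documents support a contradiction, not a settled exclusion.

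The causality section, 8.3.3.2, looks like further contradiction because it speaks of "The clinical event, including an abnormal laboratory test result". That adds little. It grades events already classed as AEs, and a symptomatic laboratory abnormality is an AE under 8.3.5, so the two can coexist.

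Nor is silent injury unwatched. Section 8.5 acts on ALT and AST values, 7.2 allows withdrawal from treatment for a laboratory abnormality, the grounds for suspension in 10.1.2 are not exhaustive, and a medical monitor oversees safety. SAP 5.1 could cover laboratory data, and SAP 5.3.4 compares coagulation factors by arm. This also stands, but none of it defines the AE record or commits to a by-arm comparison of liver tests.

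A reader might cite the mouse liver findings in Protocol 2.2.2 as proof of a silent liver signal. Liver biochemistry in that study was in the normal range, so neither AE recording nor laboratory tables would have shown it. The same section also describes a case of renal failure, so the liver is not the only organ mentioned. Its human studies report no adverse hepatic or renal effect at up to 3 g/day for 3 months, so the higher rates in the illustration are not forecasts.

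Finally, counting these events would not make the halting rule strong. At the accrual in Protocol 5.5 (two sites, 4 to 5 participants each per week), 12 participants enrol in 12/10 to 12/8 weeks, about 8 to 11 days. Most would then lack Day 7 results when the twelfth is dosed. Monitoring under Protocol 9.4.4 is continuous, so later results could still count.

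**Conclusion.** The concern holds as an internal contradiction with consequences for analysis. Section 8.3.5 conflicts with 7.1 and fits poorly with 8.3.1. Read literally, it keeps symptom-free laboratory abnormalities, including liver-test rises that meet three of the four criteria in 8.5, out of the AE-based safety endpoint and the halting count. The SAP names no laboratory analysis to make up for this.

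Two stronger readings are tempting and are not supported. One is that silent liver injury certainly counts nowhere; that depends on which section a site follows. The other is that it goes unmonitored; 8.5 provides for individual follow-up. The defect lies in recording, between-arm comparison and trial-level monitoring.

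Its size cannot be fixed from the documents. The illustration shows only the direction, and that at an assumed active-arm rate of 20% the rule would halt about one time in ten even if every event counted. That rests on the assumed rate, the six-to-six split and the events meeting the grade, attribution and 48-hour conditions.

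**What to change.** 1. In Protocol 8.3.5, item 3, remove the requirement that a clinically significant laboratory abnormality must also be symptomatic before it is recorded as an AE, so that the item agrees with 7.1 and 8.3.1. State how a case meeting an 8.5 criterion enters the AE record.

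2. Reconcile Protocol 8.3.5, 8.5 and 9.4.4 with SAP 7.6. State whether such events enter the halting count, and what the 48-hour condition on symptomatic treatment means for an event without symptoms. The content of that rule is a clinical decision for the sponsor.

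3. In SAP 5.3.6 and 7.9, add laboratory shift tables by arm at Day 7 and Day 14, with counts of participants crossing the ALT, AST and bilirubin thresholds in 8.5.

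The cost is wording in two documents and one set of tables from samples already scheduled. The downside is that somewhat more AEs will be recorded in both arms, some of them due to Covid-19 itself.

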8.3.6 SERIOUS ADVERSE EVENT REPORTING

Generally, any AE considered serious by the PI or Sub-investigator or which meets the definition of an SAE included in **Section 8.3.2, Definition of Serious Adverse Events** must be submitted on an SAE form to the Tranquil Clinical Research pharmacovigilance group (PVG).

The principal investigator or designee must immediately report to the sponsor any serious adverse event, whether or not considered drug related, including those listed in the protocol or investigator brochure and must include an assessment of whether there is a reasonable possibility that the drug caused the event [21 CFR 312.64(b)].

Upon identification, all SAEs will be reported by the site within 24 hours using the Initial SAE Report Form. The Initial SAE Report Form should be submitted Tranquil Clinical Research (CRO) within 24 hours either by e-mail (preferable) or by phone using the following contact information:

Email : [contact] [contact]

All serious adverse events (SAEs) will be followed until satisfactory resolution or until the site investigator deems the event to be chronic or the participant is stable. Other supporting documentation of the event may be requested by the study sponsor and should be provided as soon as possible.

The study sponsor will be responsible for notifying the Food and Drug Administration (FDA) of any unexpected fatal or life-threatening suspected adverse reaction as soon as possible, but in no case later than 7 calendar days after the sponsor's initial receipt of the information.

In addition, the sponsor must notify FDA and all participating investigators in an Investigational New Drug (IND) safety report of potential serious risks, from clinical trials or any other source, as soon as possible, but in no case later than 15 calendar days after the sponsor becomes aware and determines that the information qualifies for reporting.

8.3.7 REPORTING EVENTS TO PARTICIPANTS

Participants will be made aware of any significant changes in safety information that results in a change to the informed consent form. All study participants will be re-consented with the new form as soon as possible.

8.3.8 EVENTS OF SPECIAL INTEREST

This section is not applicable.

8.3.9 REPORTING OF PREGNANCY

In the event that a participant becomes pregnant while on study, study treatment will be discontinued, and a pregnancy form will be completed.

8.4 UNANTICIPATED PROBLEMS

8.4.1 DEFINITION OF UNANTICIPATED PROBLEMS (UP)

The Office for Human Research Protections (OHRP) considers unanticipated problems involving risks to participants or others to include, in general, any incident, experience, or outcome that meets all of the following criteria:

- Unexpected in terms of nature, severity, or frequency given (a) the research procedures that are described in the protocol-related documents, such as the Institutional Review Board (IRB)approved research protocol and informed consent document; and (b) the characteristics of the participant population being studied;
- Related or possibly related to participation in the research (“possibly related” means there is a reasonable possibility that the incident, experience, or outcome may have been caused by the procedures involved in the research); and
- Suggests that the research places participants or others at a greater risk of harm (including physical, psychological, economic, or social harm) than was previously known or recognized.

An incident, experience, or outcome that meets the definition of an UP noted above may warrant consideration of changes to the protocol or consent in order to protect the safety, welfare, or rights of participants or others.

